5. ENDPOINTS

For all endpoints and unless explicitly specified otherwise, Week 10 refers to Visit V8 and Week 12 refers to Visit EOT.

For handling of missing data and corresponding sensitivity analyses, see Section 6.6.

5.1 PRIMARY ENDPOINT

The primary endpoint is the total number of deregulated genes comparing baseline to posttreatment, analysed by gene expression of mucosal biopsies via RNA sequencing, per time point up to week 12.

Details on the planned analyses are given in Section 7.

5.2 SECONDARY ENDPOINTS

5.2.1 Key secondary endpoint

Not applicable. No key secondary endpoints have been specified in the CTP.

5.2.2 Secondary endpoints

5.2.2.1 Secondary efficacy endpoints

The following secondary efficacy endpoints will be analysed:

- Percent change in CRP from baseline to Week 12
- *Percent change in faecal calprotectin from baseline to Week 12*
- Percent change in faecal lactoferrin from baseline to Week 12
- Total clinical remission (defined as Total Mayo score ≤2 points, and all subscores ≤1 point) at Week 12 (cf. Section 4)

For details on calculating the total Mayo score at each visit, cf. Section 9.1.

5.2.2.2 Secondary safety endpoints

Secondary endpoint to assess safety and tolerability of BI 655130 is the number [N (%)] of patients with drug-related AEs (cf. Section 5.3 of the CTP).

TSAP for BI Trial No: 1368-0004Page 11 of 48Proprietary confidential information © 2019 Boehringer Ingelheim International GmbH or one or more of its affiliated companies

Further safety criteria 5.3.3

Intensity of adverse events will be assessed by Rheumatology Common Toxicity Criteria (RCTC) version 2.0.

Further safety criteria of interest are:

- AEs
- SAEs •

Proprietary confidential information © 2019 Boehringer Ingelheim International GmbH or one or more of its affiliated companies

- Safety laboratory values (haematology, clinical chemistry, coagulation and urinalysis)
- Physical examination
- Vital signs
- Relevant findings in 12-lead ECG
- IgE and ADA (anti-drug antibodies), as detailed in the lab manual

5.4.1 Demographic and other baseline characteristics

Standard demographic data and baseline characteristics are used as recorded in the eCRF. These include sex, ethnicity, race, age, height, weight, BMI, smoking status. Disease characteristics including time since first diagnosis, previous surgery for UC and extra intestinal manifestations will be collected during screening.

Age [years] will be determined as the difference between year of birth and year of informed consent.

BMI will be calculated as weight $[kg] / height [m]^2$ (based on the last available weight measurement prior to the first dose of BI 655130).

Time since first diagnosis [years] will be calculated as the difference between date of first diagnosis and date of informed consent, divided by 365.25. For calculation in context of incomplete information on the date of first diagnosis, cf. Section 6.6.

Proprietary confidential information © 2019 Boehringer Ingelheim International GmbH or one or more of its affiliated companies

Page 13 of 48

6. GENERAL ANALYSIS DEFINITIONS

6.1 TREATMENTS

For basic study information on the treatment to be administered, assignment to treatment, and selection of dose, cf. Section 4 of the CTP.

All patients will receive intravenous doses of 1200mg of BI 655130 solution for infusion (at V2, V5 and V7).

The following study phases are defined:

Proprietary confidential information © 2019 Boehringer Ingelheim International GmbH or one or more of its affiliated companies

Study analysis phase	Description	Start (included)	End (included)
Screening phase	Screening	Earliest of (Date of informed consent, first screening procedure)	Date/time of start of infusion of first study drug minus 1 minute.
Treatment phase & Residual effects period (REP)	On-treatment period	Date/time of start of infusion of first study drug (Day 1)	Date of end of infusion of last study drug + 140 days at 11:59 p.m.
Follow-up ¹ phase	Off-treatment period	Date of end of infusion of last study drug + 141 days at 12:00 a.m.	Latest of: i) Date of EoO visit (Week 28 visit); ii) end date on trial termination page at 11:59 p.m.

Table 6.1: 1	Flow chart	of analysis	phases
--------------	------------	-------------	--------

Dates are defined individually per patient. If more than one date is associated with a specific visit, measurements associated with a specific date are assigned to a study analysis phase according to the rules specified in the table. An analysis phase will not extend beyond the start date of the following phase.

¹ The Follow-up phase only exists if the trial completion date is after the date of end of last infusion + 140 days

CTR Section 15 AE displays will present results for the on-treatment period only. Screening and follow-up phases will not be included in this analysis.

Treatment groups for the analysis will be labelled as follows:

• "Speso 1200 mg IV BI q4w"

More details on the technical implementation of these analyses are provided in the ADS Plan of this TSAP.

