Pharmacokinetics (PK) analysis showed that exposure (AUC_{0-tz and Cmax}) to BI 655130 seems to increase with increasing dose in a greater than dose-proportional manner from 0.01 to 0.3 mg/kg while exposure increased with increasing dose in an approximately dose-proportional manner from 0.3 to 10 mg/kg. The effective half-life of BI 655130 is approximately 4 weeks in the linear dose range. Overall, PK data so far suggests target-mediated drug disposition kinetics for BI 655130. The saturation of the non-linear elimination pathway is likely occurring after 0.3 mg/kg and BI 655130 seems to exhibit linear kinetics from the next dose-level onwards. Anti-drug antibodies (ADA) were detected in 8 patients, 3 of those had pre-existing levels. However, caution should be taken in interpreting the ADA results because the drug concentrations in many ADA samples exceeded the drug tolerance level of the ADA assay (100 µg/mL). Pharmacodynamic (PD) effects in this first in human Single Rising Dose trial (c03320877) were assessed by indirect target engagement of IL-36R by BI 655130 using an ex-vivo whole blood stimulation assay. Preliminary analyses indicate that >94% peripheral IL-36R receptor occupancy is achieved with doses ≥3 mg/kg from 30 minutes post infusion to Week 10.

Boehringer Ingelheim		03 Apr 2019
BI Trial No.: 1368-0004		_
c10710598-04	Trial Protocol	Page 15 of 82

In the multiple rising dose trial (1368.2), BI 655130 or PBO have been administered to healthy male volunteers at multiple ascending i.v. doses of 3, 6 and 10 mg/kg given once a week (qw) for 4 weeks (i.e. 4 administrations), as well as a single dose cohort of 20 mg/kg. All dose groups (8 patients each, 3:1 on active or PBO) have completed dosing and 4 weeks of follow-up. Overall, BI 655130 was well tolerated. There were no AEs considered to be dose limiting and no SAEs. In all cases the AEs were of mild or moderate intensity. Furthermore, there were no clinically relevant abnormalities on treatment with BI 655130 with respect to safety laboratory, vital signs, or ECGs as assessed by a central reader.

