- Additional arguments amongst those stated before, like alternative explanation (e.g. situations where other drugs or underlying diseases appear to provide a more likely explanation for the observed event than the drug concerned).
- Disappearance of the event even though the trial drug treatment continues or remains unchanged.
- 5.3.5.2 Adverse event collection and reporting

AE Collection

The investigator shall maintain and keep detailed records of all AEs in the patient files.

The following must be collected and documented on the appropriate CRF(s) by the investigator:

- From signing the informed consent onwards until the individual patient's end of trial: all AEs (serious and non-serious) and all AESIs.
- After the individual patient's end of trial: the investigator does not need to actively monitor the patient for AEs but should only report related SAEs and related AESIs of which the investigator may become aware of by any means of communication, e.g. phone call. Those AEs should however, not be reported in the CRF.

03 Apr 2019 Page 48 of 82

Proprietary confidential information © 2019 Boehringer Ingelheim International GmbH or one or more of its affiliated companies

[figure not shown]

Figure 5.3.5.2: 1 AE reporting

The residual effect period (REP) for BI 655130, i.e., when measurable drug levels or PD effects are still likely to be present after the last administration, is 140 days (20 weeks). Therefore, all AEs reported through the REP will be considered on-treatment, cf. Section 7.3.4.

As end of REP coincides with EoO visit (last per protocol (PP) visit) in this trial, all AEs reported from first dose until end of the trial will be considered on-treatment.

AE reporting to sponsor and timelines

The investigator must report SAEs, AESIs, and non-serious AEs which are relevant for the reported SAE or AESI, on the BI SAE form via fax immediately (within 24 hours) to the sponsor's unique entry point (country specific contact details will be provided in Section 1 of the ISF). The same timeline applies if follow-up information becomes available. In specific occasions the investigator could inform the sponsor upfront via telephone. This does not replace the requirement to complete and fax the BI SAE form.

With receipt of any further information to these events, a follow-up SAE form has to be provided. For follow-up information the same rules and timelines apply as for initial information.

Information required

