7.3.4 Safety analyses

Safety will be assessed for the endpoints listed in Section 5.3. All treated patients (that is all patients who received at least one dose of the study drug) will be included in the safety analysis. In general, safety analyses will be descriptive in nature and will be based on BI standards. No hypothesis testing is planned.

Statistical analysis and reporting of AEs will concentrate on treatment-emergent AEs. To this end, all AEs occurring between start of treatment and end of the residual effect period will be considered 'treatment-emergent'. The residual effect period is defined as 140 days after the last dose of trial medication. AEs that start before first drug intake and deteriorate under treatment will also be considered as 'treatment-emergent'. Drug related AEs, as a secondary endpoint of this trial, will be tabulated by system organ class and preferred term (PT) after coding according to the current version of the Medical Dictionary for Drug Regulatory Activities (MedDRA).

In addition, the frequency, severity, and causal relationship of AEs will be tabulated by system organ class and PT after coding according to the current version of the MedDRA.

Laboratory data will be analysed both quantitatively as well as qualitatively. The latter will be done via comparison of laboratory data to their reference ranges. Values outside the reference range as well as values defined as clinically relevant will be highlighted in the listings.

Vital signs, physical examinations, or other safety-relevant data observed at screening, baseline, during the course of the trial and at the end-of-trial evaluation will be assessed with regard to possible changes compared to findings before start of treatment.

For vital signs, the differences from baseline will be evaluated. Relevant ECG findings will be reported as AEs.

Page 63 of 82

Proprietary confidential information © 2019 Boehringer Ingelheim International GmbH or one or more of its affiliated companies

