Days are counted relative to the day of treatment, which is defined as Day 1. ^A Note that measurements made at Day 1 and assigned to the on-treatment period (because mistakenly made after start of infusion of trial treatment) via assessment on date and time (i.e. safety laboratory) will not be assigned to Visit 3. Such data will be listed only.

^B Note that measurements assigned to the Week 28/EoO visit may represent follow-up measurements (off-treatment period; cf. Table 6.1: 1). Both on-treatment and off-treatment data will be included for analysis of this visit.

Repeated and unscheduled efficacy, safety and biomarker measurements will be handled similarly to scheduled measurements and will also be assigned to a time window depending upon the date of measurement.

Only one observation per time window will be selected for statistical analysis at a particular visit – the value which is closest to the protocol planned visit day will be selected. If there are two observations which have the same difference in days to the planned day, but which are not measured on the same day, the later value will be selected. If there are two observations which are both closest to the planned day and were measured on the same day, the worst value will be selected.

Assignment of observations to visits based on time windows will be based on the nonimputed (observed) data after setting values after rescue medication intake to missing (if applicable, i.e. for the "OC" approach defined in Section 6.6.2). Visits which were not assigned a value based on time windows will not be imputed in this trial.

For derivation of the last value on treatment, minimum value on treatment, and maximum value on treatment, all on-treatment values (whether or not selected in any time window; see Table 6.1: 1 for definition of the on-treatment period) will be considered; these will be derived for analysis of laboratory and vital signs data. For identification of potentially clinically significant abnormal laboratory values, all values (whether or not selected in any time window) before the off-treatment period will be considered.

Tables and figures with results of the statistical analysis will only display visits at which the respective parameter was planned to be collected according to the CTP.

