7.8.3 Vital signs

The analyses of vital signs (blood pressure, pulse rate), body temperature, and body weight will be descriptive in nature.

Descriptive statistics of vital signs over time and for the difference from baseline (see Section 6.7) will be provided by treatment using on-treatment data only, including summaries of and will include the last value during on-treatment period, the minimum value during on-treatment period, and the maximum value during on-treatment period.

Clinically relevant findings in vital signs data will be reported as baseline conditions (at screening) or as AEs (during the trial) if judged clinically relevant by the investigator, and will be analysed as such.

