7.8.4 ECG

Abnormal findings in 12-lead ECG will be reported as baseline conditions (at screening) or as AEs (during the trial) if judged clinically relevant by the investigator, and will be analysed as such. No separate listing or analysis of ECG data will be prepared.

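### The SAP closes the on-treatment period 1 to 6 days before a completer's final safety visit, so findings dated to that visit miss the AE and abnormality tables, and the documents disagree on whether they should count

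*SAP*

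**What the plan says.** **Cut-off.** SAP Table 6.1: 1 ends the combined treatment and residual effect period (REP) at "Date of end of infusion of last study drug + 140 days at 11:59 p.m" and labels everything from + 141 days off-treatment. Below the table it adds that "CTR Section 15 AE displays will present results for the on-treatment period only".

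**Visit.** The Flow Chart and SAP Table 6.7: 1 put EoO at V7 + 141 days, window + 5. The visit includes a complete physical examination, vital signs, ECG, safety laboratory tests and AE review.

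**What follows the cut-off in the SAP.**
- Section 6.7: AE frequency tables use on-treatment data only. In the search for clinically significant laboratory values, "all values (whether or not selected in any time window) before the off-treatment period will be considered".
- Section 7.8.1: AEs are assigned to a phase using the start date.
- Section 7.8.3: vital-sign statistics "will be provided by treatment using on-treatment data only".
- Section 7.8.4: ECG findings are analysed only if reported as baseline conditions or AEs. "No separate listing or analysis of ECG data will be prepared".

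**What does not follow it.** Footnote B of Table 6.7: 1 includes both on- and off-treatment data when the EoO visit is analysed. Section 7.8.2 includes follow-up in the by-visit laboratory statistics. Section 7 promises extra by-visit outputs with off-treatment data for selected displays, and lists all individual values.

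**The protocol.** Section 5.3.5.2 sets the REP at 140 days, treats its end and EoO as the same point, and concludes that "all AEs reported from first dose until end of the trial will be considered on-treatment". Section 7.3.4 limits treatment-emergent AEs to the 140-day REP. It also says that vital signs, examinations and other safety data from the end-of-trial evaluation will be compared with pre-treatment findings.

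**The concern.** EoO is the last scheduled safety assessment. The protocol text on AE reporting assumes that it falls inside the on-treatment period, but the SAP's dates put it just outside. An abnormality first arising at that visit would then be missing from the summary tables. For an ECG finding the loss is complete at summary level, because the AE tables are its only route into the analysis.

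The number of patients with drug-related AEs is a secondary endpoint (SAP 5.2.2.2). The trial plans 10 patients, with up to 4 replacements (protocol 7.7), so one patient more or less is 1/10 = 10 to 1/14 = 7.1 percentage points.

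A smaller mismatch touches the same tables. Protocol 7.3.4 says "AEs that start before first drug intake and deteriorate under treatment will also be considered" as treatment-emergent. SAP 7.8.1 states no such rule.

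**Working it through.** **Inputs.** Cut-off: last infusion + 140 days (SAP Table 6.1: 1). EoO: V7 + 141, window 0 to + 5 (Flow Chart; SAP Table 6.7: 1). V7: Day 57 ± 2, taken as the day of the last infusion. EoT: Day 85, window − 6 to + 1 (Flow Chart).

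**The documents' own figures.** The REP of 20 weeks is 20 × 7 = 140 days, as stated. As a check on day counting, FU1 at V7 + 70 is 57 + 70 = Day 127, as SAP Table 6.7: 1 gives.

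**Cut-off against visit.** Last on-treatment day = V7 + 140. EoO = V7 + 141 to V7 + 146.

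| V7 | Last on-treatment day | EoO window | EoO days on-treatment |
|---|---|---|---|
| Day 55 | 195 | 196 to 201 | 0 of 6 |
| Day 57 | 197 | 198 to 203 | 0 of 6 |
| Day 59 | 199 | 200 to 205 | 0 of 6 |

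Nominal Week 28 is 1 + 28 × 7 = Day 197, or V7 + 140, which is the last on-treatment day. The scheduled visit starts one day later. The statement in protocol 5.3.5.2 that the two dates coincide is thus off by 1 to 6 days.

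**Onset days lost.** With V7 on Day 57, the lost share of the days from first dose to EoO is 1/198 = 0.5% to 6/203 = 3.0%.

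**Who is affected.**
- *Completers who do not enter the extension trial:* always, if EoO is in window.
- *Patients who enter it:* not affected. Their EoT is also their EoO (protocol 6.2.3), at Day 79 to 86, or V7 + 22 to + 29 with V7 on Day 57.
- *Early discontinuers:* EoO is 20 weeks after the last dose. A visit on day + 140 counts; one from + 141 on does not.

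**What is affected.**
- *Outside:* AEs with onset from + 141 to EoO; EoO values in the clinically significant laboratory search; EoO values in the last/minimum/maximum and worst-grade on-treatment laboratory summaries; EoO vital signs if 7.8.3 governs.
- *Inside:* AEs reported at EoO with onset by + 140; EoO laboratory values in the by-visit tables; all listings.
- *Undetermined:* EoO vital signs by visit, because footnote B and 7.8.3 give opposite answers.

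The documents give no event rate, so the expected number of lost events cannot be computed.

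**The case against.** The strongest reply is that the SAP follows the protocol's statistical section. Protocol 7.3.4 defines treatment-emergent AEs by a 140-day REP, and SAP 6.1 uses exactly that. Protocol 5.3.5.2 also gives 140 days and refers to 7.3.4. Its wider sentence rests on the two dates being the same, whereas the rationale in global amendment 1 is that EoO should come after the REP. On this reading 5.3.5.2 was simply not updated. This stands for AEs: a reader might infer that the SAP departs from the protocol, but the protocol is itself divided. It does not settle vital signs and examinations, for which 7.3.4 names the end-of-trial evaluation.

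A reader might also infer three stronger points that the documents do not support:

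- **That everything found at EoO is lost.** Assignment follows onset, not detection, and the by-visit laboratory tables and listings keep the visit.
- **That 140 days is too short pharmacologically.** Protocol 1.2 reports that ">94% peripheral IL-36R receptor occupancy is achieved with doses ≥3 mg/kg from 30 minutes post infusion to Week 10". Carrying this forward with linear, weight-proportional kinetics and the stated 4-week half-life puts the same concentration at 21 weeks (100 kg) to 24 weeks (60 kg) after the third dose. But the occupancy statement is preliminary and comes from healthy volunteers, and protocol 2.3 expects higher clearance in UC. Assumed half-lives of 3 and 2 weeks give 15 to 18 and 10 to 11 weeks, inside the cut-off. Nor could an extension of 1 to 6 days answer a problem measured in weeks.
- **That AEs worsening from screening are dropped.** Protocol 5.3.5.2 has worsening of pre-existing conditions recorded as an AE. SAP 7.8.1 merges occurrences only when all attributes, intensity included, are identical. A worsened occurrence may therefore stand with its own start date. The absent rule is a gap in the SAP, not a demonstrated loss.

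The contrast between completers and early discontinuers is thin, since it depends on the latter being seen by day + 140.

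**Conclusion.** The point holds as a conflict over the status of the EoO visit. For every completer who stays out of the extension trial and attends in window, that visit is off-treatment by 1 to 6 days. Abnormalities dated to it leave the AE tables, the drug-related AE endpoint and the on-treatment laboratory summaries. The loss of vital-sign values is certain only if SAP 7.8.3 prevails over footnote B.

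The size is small in time, at most 3.0% of the days from first dose to EoO, and the number of patients affected is unknown because it depends on how many roll over. The matter is still worth correcting because the visit is a full safety assessment and one patient counts for 7 to 10 percentage points. The conclusion assumes that the Week 8 dose is given at V7. It needs no pharmacological assumption.

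**What to change.** Reconcile protocol 5.3.5.2, protocol 7.3.4, SAP 6.1, footnote B of SAP Table 6.7: 1 and SAP 7.8.3, by one of two routes:

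1. Define the analysis period for AEs, vital signs and abnormal laboratory values to end at the later of last infusion + 140 days and the EoO date, inclusive.
2. Keep 140 days, correct protocol 5.3.5.2, and tabulate separately the AEs and the laboratory and vital-sign abnormalities from day + 141 to EoO.

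Under either route, state in 7.8.3 whether EoO vital signs are summarised, so that it agrees with footnote B and with the end-of-trial sentence in protocol 7.3.4. In SAP 7.8.1, carry over the protocol 7.3.4 rule that an AE starting before first dose and worsening under treatment counts as treatment-emergent.

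The cost is wording plus one date derivation (route 1) or extra tabulation (route 2). No new data are needed. The downside is that AE counts may be slightly less favourable.

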6.2 IMPORTANT PROTOCOL DEVIATIONS

Data discrepancies and deviations from the CTP will be identified for all patients in the database (i.e., enrolled patients). Consistency check listings (for identification of violations of time windows) and a list of protocol deviations will be provided to be discussed at the RPM/DBLM/MQRM. At this meeting, it will be decided whether a discrepant data value can be used in analyses or whether it must be queried in the clinical database. Each protocol deviation must be assessed to determine whether it is an important Protocol Deviation (iPD). For definition of iPDs, and for the process of identification of these, refer to the BI reference document "Identify and Manage Important Protocol Deviations (iPD)" (2).

If any iPDs are identified, they are to be summarised into categories and will be captured in the RPM/DBLM/MQRM minutes via an accompanying Excel spreadsheet. The following Table 6.2: 1 contains the categories which are considered to be iPDs in this trial. If the data show other iPDs, this table will be supplemented accordingly by the time of the RPM/DBLM/MQRM. Not all iPDs will lead to exclusion from analysis sets. iPDs leading to exclusion from analysis sets are indicated as such in Table 6.2:1.

iPDs will be summarised and listed for the entered set.

TSAP for BI Trial No: 1368-0004 Page 15 of 48 Proprietary confidential information © 2019 Boehringer Ingelheim International GmbH or one or more of its affiliated companies

Category / Code	Description	Comments	Excluded from ¹
Α	Entrance criteria violated		
A1	Inclusion criteria not met		
A1.01	Age out of range	Inclusion criterion 1 Also check versus derived age	None
	LABEL: Age beyond 18-65	for patient.	
A1.02	Body weight out of range	Inclusion criterion 2	None
	LABEL: Body weight larger 100 kg	Also check versus reported body weight for patient	
A1.03	Diagnosis of UC <3 months prior to screening	Inclusion criterion 3 Also check derived time since diagnosis for patient	None
	LABEL: Diagnosis only recent		
A1.04	Moderately to severely active UC not confirmed, e.g. Mayo Score ≤ 6 and/or no elevated C-Reactive protein (CRP) or faecal calprotectin at pre-baseline visit.	Inclusion criterion 4 Also check derived total MCS,CRP and faecal calprotectin at pre-baseline	CAS
	LABEL:	Manual check in addition.	
	Disease activity not moderate or severe		

Important protocol deviations Table 6.2: 1

PV will be detected manually Source: BI reference document: "Identify and Manage Important Protocol Deviations (iPD)" [001-MCS-40-413] (2). ¹ See Section 6.3 for population definitions

TSAP for BI Trial No: 1368-0004 Page 16 of 48 Proprietary confidential information © 2019 Boehringer Ingelheim International GmbH or one or more of its affiliated companies

Category / Code	Description	Comments	Excluded from ¹
A1.05	Receiving conventional, non-biologic therapy for UC. Concurrent UC treatments need to be on stable doses:	Inclusion criterion 5	CAS #
	This therapy could consist of one or more of the following:		
	 Oral 5-ASA compound, with stable dose for at least 4 weeks prior to screening 6-MP, Methotrexate (MTX) or AZA, with stable dose for at least 8 weeks prior to screening Oral corticosteroids (≤ 20mg/day per day of prednisone or equivalent), with stable dose for at least 4 weeks prior to screening LABEL: 		
	Concurrent UC treatment not on stable dose		
A1.06	Negative colon cancer screening within the past 12 months prior to screening not available	Inclusion criterion 6	None
	LABEL:		
	Lack of negative colorectal cancer screening		
A1.07	Patients who are naïve or experienced to TNF antagonists (including infliximab, adalimumab, or golimumab) but have not failed that treatment due to primary non- response or loss of response	Inclusion criterion 7	CAS
	LABEL:		
	Patient with previous TNF experience (non- response or loss of response)		
A1.08	Women of childbearing potential did not agree to use effective method of birth control; male patients did not agree to use condoms	Inclusion criterion 8	None
	LABEL:		
	Contraception methods not used		

Important protocol deviations (continued) Table 6.2: 1

PV will be detected manually

Source: BI reference document: "Identify and Manage Important Protocol Deviations (iPD)" [001-MCS-40-413] (2) ¹ See Section 6.3 for population definitions

TSAP for BI Trial No: 1368-0004 Page 17 of 48 Proprietary confidential information © 2019 Boehringer Ingelheim International GmbH or one or more of its affiliated companies

Categor Code	у/	Description	Comments	Excluded from ¹	
Α	A1.09	Signed and dated written informed consent in accordance with GCP and local legislation prior to admission to the trial LABEL:	Inclusion criterion 9– check for tick box only. Further PVs on informed consent are defined in section B below	All	
		IC not in accordance with legislation			
A2		Exclusion criteria violated			
A	A2.01	Pregnancy	General exclusion criterion 6	None	
		LABEL:			
		Pregnancy			
A	A2.02	Patients who have previously failed treatment with any TNF antagonist (including infliximab, adalimumab, golimumab) due to primary non-response or loss of response	Gastrointestinal exclusion criterion 1	CAS	#
		LABEL:			
		Prior failure with any TNF antagonist			
A	A2.03	Extensive colonic resection, subtotal or total colectomy	Gastrointestinal exclusion criterion 4	None	
		LABEL:			
		Extensive colonic resection, or colectomy.			
A	A2.04	Ileostomy, colostomy, or known fixed symptomatic stenosis of the intestine	Gastrointestinal exclusion criterion 5	None	
		LABEL:			
		Ileostomy, colostomy, or stenosis			
Ą	A2.05	Patients who must or wish to continue the intake of restricted medications (cf. CTP Table 4.2.2.1) or any drug considered likely to interfere with the safe conduct of the trial	Gastrointestinal exclusion criterion 6	CAS	
		LABEL:			
		Use of restricted medication			

Important protocol deviations (continued) Table 6.2: 1

PV will be detected manually

Source: BI reference document: "Identify and Manage Important Protocol Deviations (iPD)" [001-MCS-40-413] (2) ¹ See Section 6.3 for population definitions

TSAP for BI Trial No: 1368-0004 Page 18 of 48 Proprietary confidential information © 2019 Boehringer Ingelheim International GmbH or one or more of its affiliated companies

Category / Code	Description	Comments	Excluded from ¹
A2.06	Evidence of infection with C. difficile or other intestinal pathogen < 30 days prior to screening	Gastrointestinal exclusion criterion 7	CAS
	LABEL:		
	Infection with intestinal pathogen		
A2.07	Currently require or are anticipated to require surgical intervention for UC	Gastrointestinal exclusion criterion 8	CAS
	LABEL:		
	Require surgical intervention for UC		
A2.08	Colonic mucosal dysplasia (moderate or	Gastrointestinal	None
	severe) or colonic adenomas	exclusion criterion 9, 10	
	LABEL:		
	Colonic mucosal dysplasia		
A2.09	Primary sclerosing cholangitis	Gastrointestinal	None
	LABEL:	exclusion criterion 11	
	Primary sclerosing cholangitis		
A2.10	Faecal transplant ≤ 6 months before screening	Gastrointestinal exclusion criterion 12	None
	LABEL:		
	Faecal transplant within 6 months		
A2.11	Disease limited to the rectum, extending <15 cm past the anal verge (ulcerative proctitis)	Gastrointestinal exclusion criterion 13	CAS
	LABEL:		
	Disease limited to the rectum		

Important protocol deviations (continued) Table 6.2: 1

PV will be detected manually

Source: BI reference document: "Identify and Manage Important Protocol Deviations (iPD)" [001-MCS-40-413] (2) ¹ See Section 6.3 for population definitions

 TSAP for BI Trial No: 1368-0004
 Page 19 of 48

 Proprietary confidential information © 2019 Boehringer Ingelheim International GmbH or one or more of its affiliated companies

Category / Code	Description	Comments	Excluded from ¹
A2.12	Relevant infectious disease or increased risk of infectious complications	Infectious Disease exclusion criterion 14, 15, 16	None
	LABEL:		
	Increased risk of infectious complications		
A2.13	Evidence of a current or previous disease or medical condition other than UC that in the opinion of the investigator is clinically significant and would make the study participant unreliable to adhere to the protocol or to complete the trial, compromise the safety of the patient, or compromise the quality of the data	General exclusion criterion 15	CAS
	LABEL: Current or previous disease leading to exclusion		
A2.14	Active or suspected malignancy or history of malignancy within 5 years prior to screening visit	General exclusion criterion 16	None
	LABEL: Malignancy within last 5 years		
A2.15	Major surgery performed within 12 weeks prior to randomization or planned during the trial	General exclusion criterion 17	None
	LABEL:		
	Recent or planned major surgery		
A2.16	Pathological safety lab parameters	General exclusion criterion 18	None #
	LABEL:		
	Pathological safety lab parameters		
A2.17	Conflicting other investigational treatment	General exclusion criterion 19	CAS
	LABEL:		
	Conflicting other treatment		

Important protocol deviations (continued) Table 6.2: 1

PV will be detected manually Source: BI reference document: "Identify and Manage Important Protocol Deviations (iPD)" [001-MCS-40-413] (2) ¹ See Section 6.3 for population definitions

TSAP for BI Trial No: 1368-0004 Page 20 of 48 Proprietary confidential information © 2019 Boehringer Ingelheim International GmbH or one or more of its affiliated companies

Category / Code	Description	Comments	Excluded from ¹	
A2.18	Known hypersensitivity to any component of the IMP	General exclusion criterion 21	None	
	LABEL: Known hypersensitivity to IMP			
A2.19	Patients who were treated with a TNF antagonist within 8 weeks prior to screening, or 3 half-lives of agent from screening, whichever is longer	Gastrointestinal exclusion criterion 2	CAS	#
	LABEL:			
	Recent TNF treatment			
A2.20	Prior use of any other biological treatment in the past (e.g. integrin inhibitors, IL12/23 or IL23 inhibitors, any other investigational biological drugs)	Gastrointestinal exclusion criterion 3	CAS	#
	LABEL:			
	Prior use of any other biologic			
В	Informed consent			
B1	Informed consent not available	Based on direct	All	
	LABEL: IC not available	assessment, not simply the tick box (which is A1.08).		
		Date of informed consent missing or no signature on patient's "Declaration of Informed Consent"		
		In this case: Patient's data will not be used at all.		
B2	Informed consent too late	Informed consent date was after Visit 1	None	
	LABEL: IC too late.			

Important protocol deviations (continued) Table 6.2: 1

PV will be detected manually Source: BI reference document: "Identify and Manage Important Protocol Deviations (iPD)" [001-MCS-40-413] (2) ¹ See Section 6.3 for population definitions

TSAP for BI Trial No: 1368-0004 Page 21 of 48 Proprietary confidential information © 2019 Boehringer Ingelheim International GmbH or one or more of its affiliated companies

Categ Code	gory /	Description	Comments	Excluded from ¹
C	, 	Trial medication and randomisation	Comments	
C C1		Incorrect trial medication		
	C1.01	Study drug medication not taken	Patient entered but no study drug taken	CAS, FAS, SAF
		LABEL:		
		Study drug medication not taken at all		
	C1.02	Incorrect medication overall	Patient who fulfills the following would be	CAS
	C1.03	LABEL: Incorrect medication Patient skipped an intermediate dose	 considered an iPD: >= 2 vials (300mg) deviation from planned dose at one visit >= 3 vials (450mg) deviation from planned dose overall Patient missing a dose at an intermediate visit	CAS
		LABEL: Patient skipped an intermediate dose.	when dose at a later scheduled visit has been taken.	
C2		Non-compliance		
D		Concomitant medication		
D1		Previous medication		
	D1.01	Washout of previous medication too short	Washout period too short -See Table 4.2.2: 1 in CTP.	CAS #
		LABEL:	011.	
		Washout too short		

Important protocol deviations (continued) Table 6.2: 1

PV will be detected manually Source: BI reference document: "Identify and Manage Important Protocol Deviations (iPD)" [001-MCS-40-413] (2) ¹ See Section 6.3 for population definitions

TSAP for BI Trial No: 1368-0004 Page 22 of 48 Proprietary confidential information © 2019 Boehringer Ingelheim International GmbH or one or more of its affiliated companies

Categ Code		Description	Comments	Excluded from ¹	
D2		Prohibited medication use			
	D2.01	Use of restricted medication as per CTP Table 4.2.2: 1 on or after Screening or during the on-treatment period when not provided as a rescue treatment to stabilize a worsening disease condition- prior to or up to Week 12	If restricted medication is initiated during trial	CAS	#
		LABEL: Restricted medication prior to week 12			
	D2.02	Use of restricted medication as per CTP Table 4.2.2: 1 when not provided as a rescue treatment to stabilize a worsening disease condition – after Week 12	If restricted medication is initiated during trial	None	#
		LABEL: Restricted medication after week 12			
D3		Change in background medication			
	D3.01	Concurrent UC treatments need to be on stable doses during treatment:	Medical review	CAS	#
		Any dose change in background medication on or after Screening or during the on- treatment period unless it is due to rescue use or adverse event– prior to or up to Week 12			
		LABEL: Concurrent UC treatment not stable prior to Week 12			
	D3.02	Any dose change in background medication period unless it is due to rescue use or adverse event – after Week 12		None	#
		LABEL:			
		Concurrent UC treatment not stable after Week 12	Medical review		

Important protocol deviations (continued) Table 6.2: 1

PV will be detected manually

Source: BI reference document: "Identify and Manage Important Protocol Deviations (iPD)" [001-MCS-40-413] (2) ¹ See Section 6.3 for population definitions

TSAP for BI Trial No: 1368-0004 Page 23 of 48 Proprietary confidential information © 2019 Boehringer Ingelheim International GmbH or one or more of its affiliated companies

	egory /		~	-	
Cod	e	Description	Comments	Excluded from ¹	
Ε		Missing data None	Missing visits, evaluations, and tests will be considered missing data, not protocol deviations		
F		Study specific analysis			
F1		Other trial specific violation			
	F1.01	Incomplete diagnosis of ulcerative colitis	Medical review	CAS	#
		LABEL: Incomplete diagnosis of UC			
F2		Certain violations of procedures used to measure primary or secondary efficacy/biomarker data			
	F2.01	To be defined at the RPM, if applicable	Manual iPDs which have a potentially relevant effect on primary or secondary data	Any exclusion will be defined at the RPM/ DBLM/ MQRM.	#
G		Other safety related violations			
	G1	Pregnancy test not done for woman of child bearing potential		None	
		LABEL: Pregnancy test not done			

Important protocol deviations (continued) Table 6.2: 1

PV will be detected manually

Source: BI reference document: "Identify and Manage Important Protocol Deviations (iPD)" [001-MCS-40-413] (2) ¹ See Section 6.3 for population definitions

Page 24 of 48

Proprietary confidential information © 2019 Boehringer Ingelheim International GmbH or one or more of its affiliated companies

